MDG + Community Rx Arm: Subjects will receive the same intervention above as well as receive vetted, personalized referrals near the subject's location to human, social and other community-based supports aligned with their diabetes goals and other needs. Beginning with the first monthly telephone care management call, the nurse will launch CommunityRx, enroll the patient, and utilize NowPow to produce a "prescription" HealtheRx that can be printed, delivered by MyChart, text message, and/or e-mail, according to the patient's preference. This will be repeated at each subsequent monthly call.

All participants in the study will receive reminders by phone, e-mail, or MyChart message for scheduling monthly calls and follow-up surveys.

Participants in all three arms will complete a baseline survey (by phone, video or online) and at 6 months and 12 months. Please see Table 1 for list of outcomes and corresponding methods to obtain the data. If needed to supplement healthcare utilization data, we will obtain health insurance claims for the participant. The informed consent process will inform study participants of the rationale for accessing these data and request participants' permission to do so, if needed.

Table 1. Outcomes and Data Collection

Aim	Outcome	Source
Aim 1	Shared decision making questionnaire ^{94,95}	Survey
	Decisional Conflict ⁹⁶	Survey
	Documentation of A1C goal	EHR
	Patient self-report of A1C goal	Survey
Aim 2	Diabetes self-efficacy ⁹⁷	Survey
	Diabetes self-care inventory ⁹⁸	Survey
	Medication adherence	Survey
	Dietary adherence	Survey
	Physical activity adherence ⁹⁹	Survey
	Knowledge and utilization of community-based resources ¹²	Survey / NowPow
Aim 3	Glucose control (A1C)	EHR or Survey
	Hypoglycemia (self-reported) ⁸¹⁻⁸³	Survey
	Hypoglycemia requiring medical assistance	EHR
	Geriatric syndromes	Survey and EHR
	Depression ¹⁰⁰	
	Falls ¹⁰¹	
	Cognitive Impairment ¹⁰²	
	Frailty ¹⁰³	
	Urine Incontinence ¹⁰⁴	
	Polypharmacy	

	Functional status Disability of (Instrumental) Activities of Daily Living ^{105,106} Lower Extremity Strength using 5-Repeated Chair Stands ¹⁰⁷ Gait speed using 8-Foot Usual Walk ¹⁰⁷	Survey
	Quality of life (SF-8) ¹⁰⁸	Survey
	ED visits and unplanned hospitalizations	EHR/Medicare claims

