- Patients unable to provide consent for themselves (specifically with a diagnosis of Alzheimer's disease and related dementias) and complete outcome assessments
- Terminal illness
- Living in an institutional setting (non-community dwelling)
- Unable to read, write, or speak English or Spanish
- Recent enrollment in My Diabetes GOAL or Community Rx Trials

I. Statistical analysis

An intention-to-treat analysis principle will be applied to all patients' outcomes, regardless of ineligibility and actual intervention provided. Multiple imputation will be used to impute missing

values for those data missing at random.¹¹² We will conduct analyses using observed data as main analyses and imputed data as part of sensitivity analyses.

Aim 1: To compare continuous outcomes such as the decisional conflict score, we will use a linear mixed model (LMM) over the three study groups. To compare processes that are binary (e.g., patients self-reporting a goal) at 12 months, a chi-squared test and a logistic regression model will be used and the latter method will adjust for patients' potential confounders such as age, gender, race, health status, and duration of diabetes. In addition, we will use the generalized estimating equations (GEE) and generalized linear mixed model (GLMM) (which may be computationally intensive) to model proportion of patients with documented goal over time (baseline and 12 months) and test the effects of treatment, time, and interaction between treatment and time.

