Aims 2 and 3: To compare self-care continuous outcomes and clinical continuous outcomes including A1C (primary outcome) over the three study groups, a repeated measure analysis of variance via LMM will be performed to model one outcome over time and test the effects of treatment, time and their interaction. Clinic will be considered as random effects in a LMM to account for within-site association. We will fit an unadjusted model first and then an adjusted model adjusting for baseline outcome and participant-level potential confounders as mentioned above. Normality will be checked and appropriate data transformation will be performed if data highly skewed. The p-value for the group comparison between MDG and MDG+CRx in A1C at 12 months will be used for the primary objective analysis at the two-sided significance level of 5% (consistent to the power justification (below)). Multiple pairwise comparisons will be conducted to compare between groups at each time point and compare the multiple time points within a group. All the multiple comparisons and analyses of all the secondary outcomes will be considered to be exploratory and will not spend the overall type I error rate of 5%. To compare each of binary outcomes such as utilization of community-based resources, we will use GEE and GLMM for group comparisons, as mentioned in analyses of Aim 1. To compare health care use (ED and hospitalizations), we will use both Poisson and negative binomial regression models. If the health care use data are zero-inflated (i.e., >50% of patients who have no service use), we will use both zero-inflated Poisson and zero-inflated negative binomial models.

Sensitivity analyses: We will also assess the impact of our interventions across patient subgroups (age group, health status, baseline A1C group, and diabetes duration with different thresholds).

Interim analyses: We will apply the statistical methods above to all the available data including baseline, all 6-month follow-up data, and about 75% 12-month follow-up data.

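### The Aim 1 logistic model for binary outcomes at 12 months does not name the baseline value of the outcome as a covariate, which can cost precision on exploratory results

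*Combined protocol and SAP*

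**What the plan says.** The Aim 1 paragraph of section I (Statistical analysis) sets out two analyses of binary outcomes.

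- At 12 months: "To compare processes that are binary (e.g., patients self-reporting a goal) at 12 months, a chi-squared test and a logistic regression model will be used". The logistic model is to "adjust for patients' potential confounders such as age, gender, race, health status, and duration of diabetes".
- Over time: GEE and GLMM are to be used "to model proportion of patients with documented goal over time (baseline and 12 months) and test the effects of treatment, time, and interaction" between the two. Only the documented goal is named here.

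In the Aims 2 and 3 paragraph, the mixed model for continuous outcomes is fitted unadjusted and then as an "adjusted model adjusting for baseline outcome and participant-level potential confounders as mentioned above". Binary outcomes in those aims are sent back to Aim 1: "we will use GEE and GLMM for group comparisons, as mentioned in analyses of Aim 1".

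On availability, Table 1 in section C gives the survey as the source of the self-reported A1C goal, and section C says "Participants in all three arms will complete a baseline survey (by phone, video or online) and at 6 months and 12 months". The document does not list survey content wave by wave, but the natural reading is that the goal item is in the baseline survey. The documented goal comes from the EHR and is itself modelled at baseline.

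The Aims 2 and 3 paragraph also makes all secondary outcomes exploratory, with no share of the 5% error rate. That covers every Aim 1 outcome.

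**The concern.** Whether a patient already had a goal at enrolment may well predict whether the patient has one a year later. Leaving a predictive baseline value out of the model makes the treatment comparison less precise than the collected data allow.

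The omission looks like an oversight. The Aims 2 and 3 paragraph names the baseline outcome as an item separate from the confounders listed under Aim 1, so the authors do not appear to regard it as part of that list.

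What is at stake is the precision of the results on goal setting, the process that My Diabetes GOAL acts on most directly.

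**Working it through.** **The plan's own figure.** There is none for Aim 1. The only sample-size calculation in the document is for the usual care arm and concerns A1C. It reproduces: 39 against 133 attention controls gives power 0.901 by the normal approximation, and 39/0.8 = 48.75, rounded up to 49. It does not bear on this point.

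**Inputs from the document.** The trial randomises 505 patients 1:1:1, so 505/3 is about 168 per arm. The 20% attrition stated for the usual care arm is borrowed here: 168 × 0.8 = 134 per arm. As a rough check, 133 of 167 attention controls (79.6%) had a 12-month A1C.

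**Inputs assumed.** The document gives no rates of having a goal at baseline or 12 months, and no association between the two. These are varied below. All tests are two-sided at 5%.

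**Route 1, formula.** Take 12-month rates of 40% and 55%, with mean 0.475. Without baseline:

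- Standard error under no difference: √(2 × 0.475 × 0.525/134) = 0.0610
- Standard error under the difference: √((0.24 + 0.2475)/134) = 0.0603
- Power = Φ((0.15 − 1.96 × 0.0610)/0.0603) = Φ(0.50) = 0.69

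Adjusting for a baseline value whose correlation with the 12-month value is φ acts roughly like raising n to n/(1 − φ²):

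| φ | Effective n per arm | Power with baseline | Gain (points) |
|---|---|---|---|
| 0 | 134 | 0.69 | 0 |
| 0.2 | 134/0.96 = 140 | 0.71 | 2 |
| 0.3 | 134/0.91 = 147 | 0.73 | 4 |
| 0.4 | 134/0.84 = 160 | 0.77 | 7 to 8 |
| 0.5 | 134/0.75 = 179 | 0.81 | 12 |

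Simulated logistic fits (3,000 trials per scenario) agree within about 3 points.

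**Route 2, simulation from a logistic model.** 134 per arm, conditional treatment log-odds 0.75, 40% of controls with a goal at 12 months, and 40% of all patients with a goal at baseline (2,000 runs per row):

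| Odds ratio of baseline for 12-month status | Power without | Power with |
|---|---|---|
| 1 | 86% | 86% |
| 3 (φ = 0.26) | 79% | 82% |
| 6 (φ = 0.41) | 70% | 80% |
| 10 (φ = 0.51) | 61% | 73% |

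Separate runs of this set-up put the gain at about 2 points for odds ratio 2, 2 to 3 for 3, 6 to 10 for 6, and 12 to 13 for 10. If only 10% have a goal at baseline, the gain is about 1 to 3 points, give or take a point of simulation error. These simulations leave out the other planned covariates.

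**Does the planned GEE/GLMM make up for it?** With 40% versus 55% at 12 months, 30% at baseline and 134 per arm, simulated power was:

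| φ | Logistic, no baseline | Logistic with baseline | Treatment-by-time test |
|---|---|---|---|
| 0.3 | 0.69 | 0.74 | 0.52 |
| 0.5 | 0.70 | 0.83 | 0.67 |

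The interaction test uses the baseline data, but in these settings it has less power than baseline adjustment.

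**The case against.** The case against making much of this is strong, and most of it stands.

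- A reader might infer that the plan excludes the baseline outcome. It does not. The covariate list opens with words that make it illustrative, so the baseline value is unnamed rather than ruled out.
- A reader might infer that all Aim 2 and 3 models adjust for baseline. Only the mixed model for continuous outcomes is written that way. Binary outcomes there refer back to Aim 1, so the plan treats binary outcomes consistently.
- Baseline data do enter one analysis of the documented goal, through the GEE/GLMM. The gap is therefore clearest for the self-reported goal. For the documented goal, what remains is that the treatment-by-time test does not generally recover the lost power.
- A reader might infer that chance imbalance distorts the result. If 40% have a goal at baseline, the SD of the difference between two arms is √(2 × 0.4 × 0.6/134) = 6.0 percentage points. Under randomisation this is ordinary chance variation, already reflected in the unadjusted standard error. It is a matter of precision, not bias.
- The loss of 12 to 13 points needs both a common baseline goal and strong persistence. The document supports neither figure.

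What the objection does not remove is that the baseline value is collected, the authors name it elsewhere, and naming it here is nearly free.

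**Conclusion.** The point holds as a minor matter of efficiency and specification. The 12-month logistic model in Aim 1 should name the baseline value of the outcome, above all for the self-reported goal.

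Under the assumptions stated, the power forgone runs from about 1 to 3 points, when few patients have a goal at baseline or the association is weak, to about 6 to 13 points, when 40% have one and the baseline odds ratio is 6 to 10. If the baseline value does not predict the 12-month value, nothing is lost. The document cannot place the trial within that range.

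The primary comparison of A1C between My Diabetes GOAL and My Diabetes GOAL + CommunityRx is unaffected. The outcomes concerned are exploratory.

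**What to change.** In the Aim 1 paragraph of section I, add the baseline value of the same binary outcome as a named covariate in the 12-month logistic model. Two short statements should go with it:

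- **Which effect is reported.** With a predictive covariate added, the treatment odds ratio is conditional on baseline status and differs from the unadjusted one even with balanced arms. The plan should say which is reported.
- **Missing baseline answers.** The main analysis uses observed data, so patients without the baseline item would drop out of the adjusted model. The multiple imputation already planned for sensitivity analyses is one way to handle them.

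The cost is a few words and no new data. Saying whether the chi-squared test or the logistic model leads would also help, but demoting the chi-squared test is optional for an exploratory outcome.

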Electronic Health records will be a critical source of data on key processes of care that are affected by My Diabetes GOAL including goal setting measures (documenting personalized goals of diabetes care, proportion following ADA recommendations, proportion choosing alternative goals) as well as referrals to care management and frequency of phone contacts. The EHR will also be the primary source of data for risk factor levels (glycosylated hemoglobin, blood pressure, cholesterol levels), medications, and health care utilization (outpatient visits, care management services, ER visits, and hospitalizations). These data are continually collected as a part of routine care. If participants receive care outside of the UChicago system during the duration of the study and their most recent A1C is not available in the EMR via Care Everywhere, we will ask the participant to self-report the A1C and offer the option for them to securely upload their results via REDCap survey link to be stored with the rest of their study data. Previously consented subjects that receive care outside of UChicago Medicine will be resent the original signed informed consent for review and asked to complete an addendum to the consent to include this upload option. All future subjects will have this upload option included in an updated informed consent. We will ask subjects for permission to access their medical records for these purposes.

Subjects will be randomized in a 1:1:1 ratio to the attention control, MDG, or MDG+CRx groups. All subjects will be asked to complete surveys upon enrollment, at 6 months, and 12 months. This will be a single-blind study, and subjects will be blinded to the different groups.

My Diabetes, My Community Study Protocol

09/16/2024

Attention control Arm: These subjects will receive monthly calls with a member of the study team.

My Diabetes GOAL Arm: Subjects will be asked to complete a survey, complete goal setting conversation with diabetes nurse, and monthly telephonic care management calls. Care management calls include review of 1) risk assessment and treatment preferences, 2) goal setting discussion 3) medication management, and referrals to hospital-based services such as diabetes education classes.

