Among the 167 patients who were enrolled in attention control arm, 133 patients had an A1C result in EHR at 12 month follow up by May of 2024. These patients had an average reduction of 0.97% (SD 1.64%) in A1C from baseline to 12 month. Based on our literature review, we found no consistent pattern for A1C change in usual care arms in behavioral intervention trials published in 2023 and 2024.¹¹⁸⁻¹²⁹ Based on this finding, we assume no A1C change will be observed in our usual care arm. By a two-sample t-test, a sample size of 39 in the usual care arm would guarantee $\geq 90\%$ power to detect at least 0.97% difference in A1C with the common SD of 1.64% between the attention control arm and usual care arm with a two-sided significant level of 5%. To account for up to 20% of subject attrition at 12 months, the final total sample size of the usual care arm is 49.

For simplicity, we plan to conduct a 1:1 matching for the usual care arm vs attention control arm (i.e., 167 patients will be included in the usual care arm). The matching procedure involves three steps. First, we identify all the potential usual care arm patients using the original eligibility criteria and have CRI generate a deidentified (except month and year of dates) list of patients at UCM excluding those who were enrolled in the study and ages over 89. Second, we will only include patients who have an A1C $\geq 7.5\%$ within our trial recruitment time (09-23-2021 to 07-07-2023). Third, we use R MatchIt package to perform the matching. We use exact matching on A1C group (7.5-8, 8-8.5, 8.5-9.5, 9.5+) and the calendar quarter using month and year when the A1C test was conducted. This step ensures patients who are enrolled in the usual care arm have similar A1C values and baseline dates as the attention control arm. We will also use propensity score matching on other covariates, such as age, gender, race/ethnicity. After the matching, we test the balance of the data on these covariates.

J. Potential risks and benefits

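### ED visit and hospitalization counts are modelled with no observation time and no end-of-observation rule, so truncated records can enter as full-year counts

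*Combined protocol and SAP*

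**What the plan says.** The analysis of ED visits and admissions (Aim 3d) is set out in Section I, Aims 2 and 3: "To compare health care use (ED and hospitalizations), we will use both Poisson and negative binomial regression models". A second rule applies when zeros are common: "If the health care use data are zero-inflated (i.e., >50% of patients who have no service use", in which case zero-inflated forms of both models are fitted. Nowhere do the documents mention an offset, person-time, a counting window, or what happens to the count when a patient's record stops.

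Table 1 in Section C gives the source as "EHR/Medicare claims". The EHR part is passive. Of the EHR items, which include ER visits and hospitalizations, Section C says: "These data are continually collected as a part of routine care". Claims are conditional: "If needed to supplement healthcare utilization data, we will obtain health insurance claims for the participant". No trigger, coverage requirement or common rule across arms is given.

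Section C foresees patients leaving the system ("If participants receive care outside of the UChicago system during the duration of the study"), but the remedy there, self-report or upload of a result, covers A1C only. Section K allows withdrawal on request and does not say whether record access continues afterwards. Section I makes observed data the main analysis, with multiple imputation as a sensitivity analysis, and treats all secondary outcomes as exploratory.

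**The concern.** A missing A1C is visible as a blank. A utilization count is not: when a patient dies or moves care, the EHR shows no further entries and the extract still returns a number. Nothing in the plan marks that number as incomplete, so multiple imputation has nothing to act on. Without an exposure term, three months of observation and twelve months carry the same weight.

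Two things follow if truncated records enter this way. Rates per patient-year are understated in any arm that loses observation time. If lost time differs between arms, the arm that loses more appears to have fewer ED visits and admissions. Short observation also adds zeros, which can help trip the switch to zero-inflated models.

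**Working it through.** **Inputs from the documents.** Follow-up is about 12 months (Section D). There are 505 patients randomized 1:1:1 (Sections B and C), so 505/3 ≈ 168 per arm. The documents give no event rate, rate ratio or power for utilization, so there is no planned figure to reproduce.

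**Assumed inputs, for illustration.** A fraction d of an arm stops being observable, and each such patient misses on average a fraction f of the year. Uniformly distributed loss gives f = 0.5; the range shown is 0.25 to 0.75. The event rate is 0.8 or 1 per year, with negative binomial dispersion 1.

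**Step 1, absolute rate.** Mean observed time = 1 − d·f. At d = 20% and f = 0.5 this is 1 − 0.10 = 0.90, so the no-offset rate is 10% too low. For f from 0.25 to 0.75 it is 5% to 15% too low.

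**Step 2, rate ratio with no true effect.** Apparent ratio (B over A) = (1 − d_B·f)/(1 − d_A·f).

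| Loss, arm A vs arm B | Mean time A, B (f = 0.5) | Ratio, f = 0.5 | Ratio, f = 0.25 to 0.75 |
|---|---|---|---|
| 20% vs 20% | 0.90, 0.90 | 1.00 | 1.00 |
| 15% vs 25% | 0.925, 0.875 | 0.946 | 0.974 to 0.915 |
| 10% vs 30% | 0.95, 0.85 | 0.895 | 0.949 to 0.838 |

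**Step 3, type I error by simulation** (168 per arm, uniform loss, no true effect). With 4,000 trials at 1 event per year, rejection at the 5% level without and with a log person-time offset was:
- equal loss: 5.2% and 5.2%
- 15% vs 25%: 6.9% and 5.5%
- 10% vs 30%: 10.7% and 5.8%

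A separate run of 1,000 trials at 0.8 events per year, fitted by negative binomial regression, agrees. At 10% vs 30% the ratio was 0.90 with 11.0% rejection without the offset, and 1.00 with 5.9% with it. Neither run fitted zero-inflated models.

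**Step 4, the zero-inflation switch.** At mean 1 and dispersion 1, the chance of no event in a full year is 1/(1 + 1) = 0.50. For a patient lost at a uniform time it is the integral of 1/(1 + t) from 0 to 1, which is ln 2 = 0.693. With 20% loss, the share of zeros is 0.8 × 0.50 + 0.2 × 0.693 = 0.54. That passes the 50% trigger, so an offset placed only in the two ordinary count models would miss the models the plan would then use.

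**Step 5, what an offset cannot do.** Let 20% leave for care elsewhere, with twice the event rate of the others. True events per patient are 0.8 × 1 + 0.2 × 2 = 1.2. Observed events are 0.8 + 0.2 × 2 × 0.5 = 1.0, so the no-offset rate is 1.0/1.2 = 0.83 of the truth, 17% too low. With person-time 0.90 the rate is 1.0/0.90 = 1.11, still 7% below 1.2.

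**The case against.** The strongest reply is that this is silence, not an error. Section I names model families in a sentence or two; nothing excludes an offset, and an analyst might well include one. That stands. A reader might infer that the plan scores lost patients as event-free, but no such rule is written. What the documents support is that nothing prevents it.

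The plan also does not ignore care elsewhere. Table 1 lists claims, Section C allows them to be obtained, and Section F provides for the payer and beneficiary identifier. This narrows the route without closing it: claims are conditional, Table 1 names Medicare alone while the text of Section C refers to health insurance generally, and inclusion starts at age 60. Nor does withdrawal from surveys or calls by itself end passive record capture.

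A reader might also infer that about a fifth of patients are lost for this outcome. Two figures tempt that reading, and neither shows it. The allowance introduced by "To account for up to 20% of subject attrition at 12 months" belongs to the sample size of the retrospective, non-randomized usual care arm, whose outcomes are A1C and medications. The other is that, of 167 attention control patients, "133 patients had an A1C result in EHR at 12 month follow up by May of 2024", leaving 34/167 = 20.4% without one. Recruitment ran to 07-07-2023, so some 12-month dates fell after May 2024, and a missing A1C does not mean hospital use went unobserved.

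Differential loss is likewise not shown. The nurse-led arms receive referrals to hospital-based services, which might hold patients in the system. The attention control calls are intended partly for retention, which might offset that.

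**Conclusion.** The gap is real: the count models have no observation time, and no rule ends observation. Because capture is passive and claims are conditional, truncated records can enter as full-year counts. If they do, absolute rates are understated, by 10% at an assumed 20% uniform loss. Rate ratios are biased only if lost time differs by arm: 1.00 for equal loss, about 0.95 for 15% versus 25%, and about 0.89 for 10% versus 30%. The loss fractions, their timing, the event rate and the dispersion are all assumptions, so these figures show sensitivity and do not estimate the bias in this trial.

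It would go too far to say that the trial's conclusions are at risk. The primary A1C comparison is untouched, and this outcome is exploratory and outside the 5% error rate. Exploratory status does not make a biased estimate useful, however, and the remedy is standard. The point is of modest importance.

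**What to change.** In Section I, Aims 2 and 3:

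- Define each patient's observation period as ending at the earliest of 12 months, death, withdrawal of record access, or documented transfer of care without claims cover.
- Use the log of observed person-time as an offset in the Poisson and negative binomial models and in the count part of both zero-inflated models.
- State when claims are obtained, by the same rule in all arms.
- Report person-time and deaths by arm beside the rates, since an arm with more deaths has less time in which to accrue visits.

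The cost is a few sentences, one end-of-observation date per patient, and slightly wider intervals. Dating transfers of care is the real work. Transfers that leave no trace will still count as full person-time, and an offset does not correct for sicker patients leaving. A sensitivity analysis addressing deaths and patients without claims cover would show how far that matters.

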Usual care for diabetes at the University of Chicago is constantly evolving and has features that are important to describe and acknowledge. Since 2018, [name] has been co-chair for diabetes quality improvement at University of Chicago Medicine. University of Chicago has high rates of poor diabetes control based on the quality measure of A1C>9.0%. To reduce rates of poor control, the ambulatory quality improvement team has: 1) conducted system wide outreach to patients to get an A1C test, 2) installed Best Practice Alerts to remind physicians to order lab tests for diabetes, 3) installed point of care testing to primary care clinics, 4) created new drug prescribing SmartSet modules, and 5) organized and vetted patient education materials. University of Chicago also has diabetes education programs, a specialized pharmacist designated to solve problems with high drug prices. This collection of interventions has been associated with steady decline in the rates of poor control (29.2% in April 2019 to 26.6% in March of 2020).

To reduce the chance that benefits from the My Diabetes GOAL arms are due to attention alone, we will also conduct monthly calls to attention control subjects but will not discuss specific issues related to diabetes care. These calls will also help to ensure retention of attention control subjects in the study.

To reduce bias, we will blind participants to the arm of the intervention at the time of enrollment.

H. Type and number of experimental subjects

Individuals will be contacted for enrollment using methods described below in Section P. Recruiting Methods. Individuals will be contacted, screened for inclusion, recruited for study participation and participate in the informed consent process. We plan to enroll up 517 patients (12 in the pilot, 505 in the RCT). We will determine trial arm assignment through a random number generator. Patients will be blinded to study hypotheses and will be unaware of allocation. Our data analyst will be blinded to the treatment allocation of patients.

Inclusion Criteria:

- Males and females 60 years of age or older
- A1C 7.5% or greater
- Clinical encounter at UChicago practice in prior year
- Have access to a cell phone and provides the research interviewer with the cell phone number with internet access OR have a personal email address.

Exclusion Criteria:

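### The count models for ED visits and unplanned hospitalizations name no covariate; an adjusted model with each patient's prior-year count would cheaply recover some precision in this exploratory comparison

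*Combined protocol and SAP*

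**What the plan says.** ED visits and unplanned hospitalizations are outcome 3d in Section B. Table 1 in Section C gives their source as the EHR or Medicare claims.

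The analysis is in Section I, in the paragraph on Aims 2 and 3: "To compare health care use (ED and hospitalizations), we will use both Poisson and negative binomial regression models". The next sentence moves to zero-inflated Poisson and zero-inflated negative binomial models under this condition: "If the health care use data are zero-inflated (i.e., >50% of patients who have no service use". Neither sentence names a covariate or a baseline period.

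Earlier in that paragraph is the adjustment rule: "We will fit an unadjusted model first and then an adjusted model adjusting for baseline outcome and participant-level potential confounders as mentioned above". It falls between the sentence on clinic as a random effect in the linear mixed model and the sentence on checking normality. That block opens with its scope: "To compare self-care continuous outcomes and clinical continuous outcomes including A1C (primary outcome) over the three study groups". The confounders it points back to are in the Aim 1 paragraph: "potential confounders such as age, gender, race, health status, and duration of diabetes". Binary outcomes are expressly sent back to the Aim 1 methods; counts are not.

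On data, Section C makes the EHR the primary source for utilization, including "ER visits, and hospitalizations). These data are continually collected as a part of routine care". Section H makes a prior-year visit an inclusion criterion: "Clinical encounter at UChicago practice in prior year". Section I classes all secondary outcomes as exploratory, outside the 5% type I error.

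**The concern.** Use of emergency and inpatient care is typically skewed, and a few habitual high users can dominate the mean of an arm of about 168 patients (505/3). Section H describes allocation only as a random number generator and states no stratification, so a chance imbalance in high users would go uncorrected. A patient's own earlier count is a natural predictor of the later one. Leaving it out keeps stable differences between patients in the error term and widens the interval of each rate ratio.

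The plan already applies this principle to its continuous outcomes. For counts it neither states an adjusted model nor says what a baseline value would be, so an analyst could not carry out the adjustment from the text. What is at stake is precision and power for one named aim.

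**Working it through.** **1. Is a prior-use covariate specified?** The three outcome types in the Aims 2 and 3 paragraph compare as follows.

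| Outcome type | Model | Adjustment stated |
|---|---|---|
| Continuous | Linear mixed model | Unadjusted, then adjusted for baseline outcome and confounders |
| Binary | GEE and GLMM | Referred back to Aim 1 |
| Count (ED, hospital) | Poisson, negative binomial, zero-inflated versions | None stated |

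The confounder list is age, gender, race, health status and diabetes duration. Prior use is not on it.

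**2. Could the covariate be obtained?** For in-system care, it should be. The EHR records these events continually, and each participant had contact with the system in the year before entry. The retrospective usual-care extraction in Section I starts on 9-23-2020, a year before recruitment opened on 09-23-2021. It covers A1C and medications only, but it shows that a pre-enrollment pull over that period is considered workable.

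**3. Is there a plan figure to reproduce?** No. The documents give no rate, effect, dispersion, correlation or power for utilization. The sample-size calculation in Section I concerns A1C in the usual care arm and does not bear on this point.

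**4. Size under assumptions.** Two separate simulations compared two arms of 168, with an assumed rate ratio of 0.65 and a two-sided 5% test. Negative binomial regression was fitted without and with the prior-year count. Simulation A used lognormal patient frailty and log(1 + prior count), with 600 runs per setting. Simulation B used gamma frailty and log(1 + prior count) plus an any-use indicator, with 400 runs per setting. Control means were 0.5 or 1.0 per year. Power is the share of runs that rejected.

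| Correlation of yearly counts | Simulation | Power without | Power with | Gain (points) |
|---|---|---|---|---|
| 0.11 | A | 60.3% | 60.8% | 0.5 |
| 0.11 | B | 42.7% | 45.5% | 2.8 |
| 0.15 | B | 72.3% | 71.8% | -0.5 |
| 0.16 | B | 47.7% | 48.7% | 1.0 |
| 0.26 | B | 49.2% | 51.5% | 2.3 |
| 0.27 | A | 49.5% | 53.0% | 3.5 |
| 0.33 | B | 66.2% | 70.3% | 4.1 |
| 0.37 | B | 45.5% | 50.2% | 4.7 |
| 0.38 | A | 67.3% | 72.3% | 5.0 |
| 0.39 | A | 47.4% | 54.3% | 6.9 |
| 0.42 | A | 77.0% | 82.0% | 5.0 |
| 0.43 | B | 50.4% | 58.1% | 7.7 |
| 0.51 | B | 64.7% | 75.0% | 10.3 |
| 0.53 | A | 66.2% | 76.3% | 10.1 |
| 0.64 | B | 50.5% | 60.5% | 10.0 |

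Differences of a point or two are within simulation noise. Counted rejections are used because the model-based standard error can flatter the adjustment. In the last row it fell from 0.224 to 0.181, a variance cut of 1 - (0.181/0.224)^2 = 35%. The actual spread of the estimates fell only from 0.215 to 0.196, which is 1 - (0.196/0.215)^2 = 17%.

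**5. Smaller effects.** Approximate power is Phi(|ln RR|/SE - 1.96). Take SE = 0.20, within the simulated range of 0.18 to 0.23, and the largest variance reduction in simulation A, 21%. The adjusted SE is 0.20 x sqrt(0.79) = 0.178.
- RR 0.65: 0.431/0.20 gives 58%; 0.431/0.178 gives 68%.
- RR 0.80: 0.223/0.20 gives 20%; 0.223/0.178 gives 24%.
- RR 0.85: 0.163/0.20 gives 13%; 0.163/0.178 gives 15%.

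**6. What these figures leave out.** The comparator had no covariates at all, so the gain over a model already containing health status was not estimated and should be smaller. In simulation B, 59% to 74% of patients had no events. Under those assumed rates the plan's 50% rule would bring in the zero-inflated models, and the figures above are for the plain negative binomial.

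**The case against.** The plan is silent on covariates for counts; it does not exclude them. The adjustment sentence stands under the same Aims 2 and 3 label, and a generous reader could extend it to every outcome there. A reader might infer that the plan has decided against adjustment, and the text does not support that. The gap remains, however: even if the sentence is extended, no look-back period says what the baseline count is. The lack of a baseline survey item is not the obstacle, since A1C is also taken mainly from the EHR.

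A reader might also infer a biased comparison or a threat to the trial's main result. Neither follows. Randomization keeps the contrast unbiased on average, the outcome is exploratory, and no power target is set for it.

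A third temptation is the simple 1 - rho^2 rule. At rho = 0.5 it cuts variance by 25% and lifts 80% power to about 90%. It is optimistic here: at a correlation of 0.53 it takes 66.2% to 80.1%, where simulation gave 76.3%; at 0.42 it takes 77.0% to 84.5%, where simulation gave 82.0%.

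Two practical objections stand. One required encounter does not show that prior use is fully captured: Section C recognizes outside care, and claims are obtained only if needed. The change would also come late. Recruitment ran to 07-07-2023, so 12-month follow-up would have ended by about 07-07-2024, before the final version of 11/15/2024. In mitigation, utilization is not among the interim outcomes listed in Section C, and Section H says the analyst is blinded to allocation.

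**Conclusion.** The point holds as a modest, inexpensive improvement. The count models for ED visits and hospitalizations are specified without covariates, and nothing in the text defines a baseline count for them. The cost of fitting them that way is precision in an exploratory comparison; validity, type I error and the A1C analysis are unaffected.

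The size cannot be derived from the documents. Under the assumptions shown, the gain is roughly nil at a weak year-to-year correlation and about 5 to 10 power points at a count correlation of about 0.4 to 0.5 with a rate ratio of 0.65. It shrinks to about 2 to 4 points at rate ratios of 0.85 to 0.80, and further if health status is already in the model. Confidence in the direction is good; confidence in any single figure is low.

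**What to change.** In Section I, Aims 2 and 3, keep the Poisson, negative binomial and zero-inflated families and add after the health care use sentences:

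- After the unadjusted model, an adjusted model will include log(1 + number of the same events in the 12 months before randomization), taken from the same data source in all arms, plus the participant-level covariates already listed.
- If a zero-inflated model is used, the prior count will enter both the count part and the zero part.
- The unadjusted rate ratio will be reported as well.

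Fix and date this before anyone sees unblinded utilization results.

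The cost is a short SAP addition and a 12-month look-back in the EHR extraction, and in the claims if these are used. No new patient contact is needed. Prior care outside the system will be under-counted where only the EHR is used. That weakens the covariate but does not bias the randomized contrast.
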